12.2 AE CODING DICTIONARY

AE coding for this study will be done per International Medical Device Regulators Forum (IMDRF) AE Terminology Annex E – Clinical Signs, Symptoms and Conditions.

CONFIDENTIAL AND PROPRIETARY

Study Protocol	Smith-Nephew
A Prospective, Multi-center, Randomized Controlled	Number:
Study to Evaluate the Safety and Efficacy of ARCR	REGENETEN.2020.01
augmented with REGENETEN™ Bioinductive Implant	Version: 2.0, 08 Dec
System in Full-thickness Tears (large or massive) Repair	2021
versus ARCR alone	Page: 80 of 134

12.3 Reporting Procedures

AE of any kind and DD will be recorded in the applicable eCRF and source notes. The Investigator will evaluate all AE for relationship to the device and procedure, seriousness, and severity. DD will be evaluated for potential to cause SADE. The following timescales should be followed for the AE/DD information to be entered into the eCRF and reported to the Sponsor or designee (see Figure 12.3-1 and Figure 12.3-2):

- ADE and DD without unreasonable delay
- SAE, SADE and DD with potential to cause SADE immediately (i.e. within 24 hours of the investigator being informed about the event)

For ADE and DD, details of the product/procedure related to the event will be included and where applicable, pictures taken of the device. The deficient product should be retained for return to Smith+Nephew unless it is contaminated (e.g., used dressings must not be retained). Updates to submitted information will be recorded in the eCRF according to the timescales above.

All adverse events will be reviewed by a medically qualified person appointed by the Sponsor to determine which, if any, meet criteria for expedited reporting to the regulatory authorities.

[figure not shown]
The investigator will inform the IRB/EC of adverse events according to the IRB/EC requirements.

Depending on the nature of the adverse event, Smith+Nephew may request copies of the subject's medical records, Imaging, Operative notes, as well as results of any relevant laboratory tests performed or other documentation related to the AE. If the subject was hospitalized, a copy of the discharge summary may be requested by Smith+Nephew and should be forwarded as soon as it becomes available. In certain cases, Smith+Nephew also may request a letter from the Investigator that summarizes the events related to the case. Refer to the ISF Sponsor Contact Information Sheet to report SAE, unanticipated SADE, anticipated SADE, and DD.

CONFIDENTIAL AND PROPRIETARY

[figure not shown]
Study Protocol	Smith-Nephew
A Prospective, Multi-center, Randomized Controlled	Number:
Study to Evaluate the Safety and Efficacy of ARCR	REGENETEN.2020.01
augmented with REGENETEN™ Bioinductive Implant	Version: 2.0, 08 Dec
System in Full-thickness Tears (large or massive) Repair	2021
	Page: 81 of 134

Figure 12.3-1: Evaluation and Reporting of Adverse Events

Study Protocol	Smith-Nephew
A Prospective, Multi-center, Randomized Controlled	Number: REGENETEN.2020.01
Study to Evaluate the Safety and Efficacy of ARCR augmented with REGENETEN™ Bioinductive Implant	Version: 2.0, 08 Dec
System in Full-thickness Tears (large or massive) Repair	2021
versus ARCR alone	Page: 82 of 134

Figure 12.3-2: Evaluation and Reporting of Device Deficiencies

12.4 UNBLINDING OF INVESTIGATIONAL PRODUCT

Not applicable.

12.5 FOLLOW-UP OF SUBJECTS WITH ADVERSE EVENTS

For subjects who are experiencing ongoing unresolved AE at the time of their study completion or early discontinuation from the study, it is recommended that the Investigator schedule an appropriate follow-up visit to determine the outcome of the event.

Any additional data must be documented and available to the Sponsor who will determine whether the data need to be documented in the eCRF/Clinical Study Report.

CONFIDENTIAL AND PROPRIETARY

Study Protocol	Smith-Nephew
A Prospective, Multi-center, Randomized Controlled	Number:
Study to Evaluate the Safety and Efficacy of ARCR	REGENETEN.2020.01
augmented with REGENETEN™ Bioinductive Implant	Version: 2.0, 08 Dec
System in Full-thickness Tears (large or massive) Repair	2021
versus ARCR alone	Page: 83 of 134

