7.8.2 Withdrawal from Study

The Investigator may withdraw subjects from the study for many reasons, including but not limited to the following:

- subject noncompliance (e.g., did not follow instructions)
- subject lost to follow-up
- safety reasons (e.g., AEs, ADEs, SAEs)
- if the Investigator or the Sponsor stops the study for any reason and decides to withdraw subject(s) from the study
- concurrent illness
- any other significant reason identified by the Investigator.

For each case, information will be obtained in the source document and the eCRF, detailing circumstances leading to the withdrawal. Data collected upon point of withdrawal will be included as study data.

Subjects who drop out or are withdrawn will not be re-entered into the study at a later date.

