10.5 SAFETY ANALYSES

All safety endpoints will be summarized using the safety population.

Adverse Events

The number of subjects reporting: adverse events, serious adverse events, adverse device effects, serious adverse device effects, and unanticipated serious device effects will be summarized. In addition, for each adverse event, the following will be summarized: severity, the relationship to investigational device use, outcome and duration of the resolved adverse events and the duration of the adverse events at trial discontinuation.

Device deficiencies

The number of device deficiencies and the number of patients reporting a device deficiency will be summarized as well as a summary of device deficiencies with the potential to cause SADE.

Additional summaries of safety endpoints, if applicable, will be described in the SAP.

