12.1.3 Serious Adverse Events and Serious Adverse Device Effects

An AE or ADE is considered a **Serious** Adverse Event (SAE) or **Serious** Adverse Device Effect (SADE) if, in the view of either the Investigator or the Sponsor, it led to any of the following:

- a) death,
- b) serious deterioration in the health of the subject, users or other persons as defined by one or more of the following:
 - 1) a life-threatening illness or injury, or
 - 2) a permanent impairment of a body structure or a body function including chronic disease, or
 - 3) in-patient or prolonged hospitalization, or
 - 4) medical or surgical intervention to prevent life-threatening illness or injury or permanent impairment to a body structure or a body function,
- c) foetal distress, foetal death or a congenital abnormality or birth defect including physical or mental impairment.

CONFIDENTIAL AND PROPRIETARY

Study Protocol	Smith-Nephew
A Prospective, Multi-center, Randomized Controlled	Number:
Study to Evaluate the Safety and Efficacy of ARCR	REGENETEN.2020.01
augmented with REGENETEN™ Bioinductive Implant	Version: 2.0, 08 Dec
	2021
versus ARCR alone	Page: 78 of 134

Note: Planned hospitalization for a pre-existing condition, or a procedure required by the study protocol, without serious deterioration in health, is not considered a serious adverse event.

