12.5.1 Ongoing Adverse Events at Study Discontinuation

AEs which are **related** to a study procedure or REGENETEN Implant system and are ongoing at end of the subject's participation: The event should be followed until it is either resolved or until the event has become chronic and is not expected to further improve based on the Investigator's review of the event.

AEs which are **not related** to a study procedure or REGENETEN Implant system and are ongoing at end of the subject's participation should be followed for 30 days after discontinuation or if the AE is resolved, whichever is sooner.

At the time of data analysis (e.g., interim or final), an evaluation of ongoing events should take place and be listed as ongoing in the safety table.

CONFIDENTIAL AND PROPRIETARY

Study Protocol	Smith-Nephew
A Prospective, Multi-center, Randomized Controlled	Number:
Study to Evaluate the Safety and Efficacy of ARCR	REGENETEN.2020.01
augmented with REGENETEN™ Bioinductive Implant	Version: 2.0, 08 Dec
System in Full-thickness Tears (large or massive) Repair	2021
versus ARCR alone	Page: 84 of 134

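### Section 12.5 lets the Sponsor decide, without criteria, whether AE follow-up obtained after exit is recorded, in conflict with sections 12.3 and 12.5.1

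*Combined protocol and SAP*

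**What the plan says.** Section 12.5 applies to subjects whose adverse event is unresolved when they complete the study or leave it early. For them "it is recommended that the Investigator schedule an appropriate follow-up visit to determine the outcome of the event". Whatever this yields must be documented and made "available to the Sponsor who will determine whether the data need to be documented in the eCRF/Clinical Study Report".

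Section 12.5.1 sets the follow-up. For an event related to a study procedure or the implant, "The event should be followed until it is either resolved or until the event has become chronic and is not expected to further improve", on the Investigator's review. An unrelated event "should be followed for 30 days after discontinuation or if the AE is resolved, whichever is sooner". Events open at an interim or final analysis are to be evaluated and shown as ongoing in the safety table.

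Section 12.3 puts every adverse event into the eCRF and source notes, and requires later changes to reported information to be entered in the eCRF on the same timescales. For serious events and serious device effects the limit is 24 hours from when the investigator is informed.

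Section 10.5 plans counts of subjects with AEs, SAEs, ADEs, SADEs and unanticipated serious device effects. For each event it also summarises severity, relationship, and the "outcome and duration of the resolved adverse events and the duration of the adverse events at trial discontinuation".

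**The concern.** The protocol asks sites to obtain an outcome after exit and then makes recording it optional. The choice is made with the outcome in hand. Section 8.2.2 says the study is not blinded, so the treatment arm can be known as well. Section 12.5 does not limit the discretion by seriousness, relatedness, reason for exit or date.

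The subjects most exposed are those who leave because of an adverse event that is still open, since section 7.8.2 allows withdrawal for AEs, ADEs and SAEs. For them the final outcome can come only from this follow-up.

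Seriousness is also involved. One criterion in section 12.1.3 is "a permanent impairment of a body structure or a body function including chronic disease". An event closed under 12.5.1 as chronic and not expected to improve may therefore need re-assessment as serious. Section 12.5 does not ask for that re-assessment.

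At stake are the outcome, duration and serious-event summaries in 10.5, in a trial meant to support registration in China and post-market follow-up (Synopsis; section 8.1).

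**Working it through.** No arithmetic applies, because the point concerns a recording rule. The check sets the sections side by side.

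1. **What is certainly recorded before exit.** The event, its seriousness, severity and relationship are evaluated and recorded under 12.3. The circumstances of withdrawal go into the eCRF, and data up to withdrawal count as study data (7.8.2). A full Exit Visit should be done where possible for subjects who stop early (9.1.12). The Sponsor has no choice over any of this.

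2. **What falls under 12.5.** Only information obtained after exit on an event still open at exit. After withdrawal of consent no further data may be collected (7.8.4), so any gap there does not come from 12.5.

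3. **Section 12.3 against 12.5.** An outcome learned after exit is a change to an event already reported. Under 12.3 it goes into the eCRF. Under 12.5 it goes in if the Sponsor so decides. Both rules cannot govern the same item. Because 12.5 is the specific rule for the period after exit, a site or data manager could reasonably follow it.

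4. **Section 12.5.1 against 12.5.** Section 12.5 only recommends a visit, whereas 12.5.1 says the event should be followed to a defined end. Section 12.5.1 does not say where the result is recorded, so 12.5 decides whether that follow-up reaches the database.

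5. **Effect on 10.5 if the follow-up is not entered.**
   - An event that resolves after exit stays in the unresolved group, and its duration stops at exit.
   - A related event confirmed as chronic looks the same in the table as a minor complaint awaiting closure, since both are ongoing.
   - An event that becomes permanent or serious after exit keeps its exit classification unless the 12.3 route is followed, and the SAE or SADE count would then miss it.

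6. **Size.** The documents give no expected number of events open at exit and no rate of later change. The denominator is not simply the 130 randomised device subjects either. Section 10.2 defines the safety set by receipt of the device, and up to 40 revision subjects also receive it (8.2.1), so the planned figure is up to 130 + 40 = 170. Any rate would rest on an assumed numerator, so none is given.

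**The case against.** The strongest reply is that 12.3 already settles the matter. It requires changes to be entered and serious events to be reported within 24 hours of the investigator being informed, and section 21.5 separately obliges the Principal Investigator to record every adverse event and report serious ones. Under 12.1.3 either the Investigator or the Sponsor can judge an event serious, so the Sponsor alone cannot keep it non-serious. This limits the concern considerably, above all for events that become serious. It does not remove it, because 12.5 still gives a contrary instruction for the same data. Also, the timescales listed in 12.3 do not name non-serious, unrelated events, so its rule on updates is least clear for those.

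A reader might infer that adverse events, or chronic ones in particular, can vanish from the safety results. The documents do not support that: the event is already in the eCRF, and 12.5.1 keeps open events visible as ongoing. Nor do they support the inference that every subject withdrawn for safety lacks a recorded outcome, since some events will have resolved by the Exit Visit. A reoperation during the study is captured on its own form, follow-up continues, and later data are presented separately as safety data (7.8.1). Only surgery after exit could be affected.

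A reader might also infer that favourable outcomes would be added and unfavourable ones left out. No section describes such a practice. The defect is a discretion without criteria, which is not evidence of selective entry.

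Finally, 10.5 leaves additional safety summaries to the SAP, and the reporting flowchart (Figure 12.3-1) is not visible in the text reviewed. Either may clarify the practice, but the sentence in 12.5 would still need to agree with it.

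**Conclusion.** The point holds as a conflict between recording rules. Section 12.5 gives the Sponsor an outcome-aware and potentially arm-aware choice over post-exit AE data, against the mandatory updating in 12.3 and the purpose of the follow-up in 12.5.1. The possible loss is confined to what is learned after exit about events open at exit. It does not extend to the events themselves.

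This rests on two readings: that an AE outcome obtained after exit is an update within the meaning of 12.3, and that the additional data in 12.5 include the follow-up called for in 12.5.1. Both are the natural readings. No magnitude is claimed. The change is still worth making, because it removes an avoidable choice from the safety summaries at little cost.

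**What to change.** Delete the sentence giving the Sponsor discretion and reconcile 12.5 with 12.3 and 12.5.1. Replacement text could read:

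> For subjects who have not withdrawn consent (section 7.8.4), all follow-up data called for by section 12.5.1 on adverse events open at exit will be entered in the eCRF up to database lock. They will be summarised by arm as status at exit and status at last follow-up. An event that becomes chronic or permanent will be re-assessed against section 12.1.3 and reported within the timescales of section 12.3.

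Carry the two-status table into 10.5 and the SAP. State its denominators, because the safety set in 10.2 is worded by device receipt, and say how outcomes received after lock are reported.

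The change concerns recording only. The follow-up periods, seriousness criteria and reporting timescales stay as they are. The cost is one protocol paragraph, use of the existing AE form, and a few more AE updates and queries after exit.

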12.5.1 Ongoing Adverse Events at Study Discontinuation

AEs which are **related** to a study procedure or REGENETEN Implant system and are ongoing at end of the subject's participation: The event should be followed until it is either resolved or until the event has become chronic and is not expected to further improve based on the Investigator's review of the event.

AEs which are **not related** to a study procedure or REGENETEN Implant system and are ongoing at end of the subject's participation should be followed for 30 days after discontinuation or if the AE is resolved, whichever is sooner.

At the time of data analysis (e.g., interim or final), an evaluation of ongoing events should take place and be listed as ongoing in the safety table.

CONFIDENTIAL AND PROPRIETARY

Study Protocol	Smith-Nephew
A Prospective, Multi-center, Randomized Controlled	Number:
Study to Evaluate the Safety and Efficacy of ARCR	REGENETEN.2020.01
augmented with REGENETEN™ Bioinductive Implant	Version: 2.0, 08 Dec
System in Full-thickness Tears (large or massive) Repair	2021
versus ARCR alone	Page: 84 of 134

13. INVESTIGATOR OBLIGATIONS

The Principal Investigators will comply with Good Clinical Practice (GCP), and all applicable regulatory requirements as outlined in Appendix 21.5 and 21.6 of this protocol. In addition, the PI will ensure that the Financial Disclosure Statements will be completed by the PI and the Sub-Investigator upon entry into the study and as any changes that affect their financial disclosure status occur during the course of the study and up to one year after study completion.

14. SPONSOR AND MONITOR RESPONSIBILITIES

The Sponsor will designate a monitor to conduct the appropriate site visits at the appropriate intervals. The clinical investigation will be monitored to ensure that: the rights and wellbeing of the subjects are protected; the reported data are accurate, complete, and verifiable from the source documents; and the study is conducted in compliance with the currently approved protocol and amendment(s), if applicable, with GCP regulations, and with applicable regulatory requirements.

Detailed monitoring requirements will be documented in the Clinical Monitoring Plan for this study.

14.1 SITE QUALIFICATION VISIT

A site qualification visit may be performed by the Sponsor prior to the execution of a clinical agreement to ensure that all Investigators have the appropriate training, staff, facilities, and resources to adequately conduct the study.

CONFIDENTIAL AND PROPRIETARY

Study Protocol	Smith-Nephew
A Prospective, Multi-center, Randomized Controlled	Number:
Study to Evaluate the Safety and Efficacy of ARCR	REGENETEN.2020.01
augmented with REGENETEN™ Bioinductive Implant	Version: 2.0, 08 Dec
System in Full-thickness Tears (large or massive) Repair	2021
versus ARCR alone	Page: 85 of 134

14.2 SITE INITIATION VISIT

A site initiation visit to provide training on the specifics of the study, site obligations and expectations of study conduct will be performed by the Sponsor or qualified person designated by the Sponsor following the execution of the CTA and documented IEC approval.

14.3 Sponsor Audits and Regulatory Inspection

Quality Assurance auditors, whether an employee of the Sponsor or its designee, may evaluate study conduct at the study sites. These parties must have access to any and all study reports and source documentation, regardless of location and format.

14.4 CLOSE-OUT VISIT

A study close-out visit will be performed by the Sponsor or designee to retrieve and account for all remaining clinical data and to resolve outstanding queries. During study close-out, the monitor will review investigator files to ensure required documents and records are on file, confirm the disposition of any other ancillary items used for the study, and review regulatory requirements regarding records retention and IEC reporting requirements. When no subjects have been included, a remote close-out visit may be conducted.

15. PROTOCOL AMENDMENTS

Amendments should be made only in necessary cases once the study has started. Protocol amendments must be approved by the protocol signatories prior to submission to the IRB/IEC. Protocol amendments need to be approved by the IRB/IEC and Regulatory Authority(ies), according to the applicable requirements prior to implementation at the site.

16. CONFIDENTIALITY OF THE STUDY

The confidentiality of this study and associated documents is governed by the terms of the Clinical Trial Agreement (CTA).

CONFIDENTIAL AND PROPRIETARY

Study Protocol	Smith-Nephew
A Prospective, Multi-center, Randomized Controlled	Number:
Study to Evaluate the Safety and Efficacy of ARCR	REGENETEN.2020.01
augmented with REGENETEN™ Bioinductive Implant	Version: 2.0, 08 Dec
System in Full-thickness Tears (large or massive) Repair	2021
versus ARCR alone	Page: 86 of 134

17. STATEMENTS OF COMPLIANCE

This clinical study will be performed in compliance with the ethical principles of the Declaration of Helsinki and ISO14155:2020 Clinical investigation of medical devices – Good Clinical Practice (GCP) [37, 38, 46], and all applicable local Singapore, Hong Kong, China, United Kingdom, Germany, Switzerland, France, Canada, United States, Australia, New Zealand, Japan and Netherlands regulations.

This clinical study will not commence until the required approval/favorable opinion from the IRB/IEC and/or regulatory authority has been obtained. Any additional requirements imposed by the IRB/IEC and/or regulatory authority will be followed.

Public/Products Liability Insurance has been purchased by Smith+Nephew plc. Worldwide and incorporates coverage for personal injury in respect of clinical studies. The Sponsor agrees to operate in good faith and in accordance with ABHI (Association of British Healthcare Industries) guidelines regarding compensation for injury arising in the course of clinical studies.

18. END OF STUDY

Should circumstances arise which require the termination of the entire study prior to its planned completion (e.g., safety concerns) or circumstances arise which mean the end of the participation of an individual site (e.g., departure of Investigator, non-compliance), then this will be undertaken according to the SOPs of the Sponsor.

This study may be temporarily suspended or prematurely terminated if there is sufficient reasonable cause. Written notification, documenting the reason for study suspension or termination, will be provided by the suspending or terminating party to other parties (Investigator, IRB/IEC, Sponsor and regulatory authorities). If the study is prematurely terminated or suspended, the Investigator will promptly inform the IRB/IEC and the study sites, and will provide

CONFIDENTIAL AND PROPRIETARY

Study Protocol	Smith-Nephew
A Prospective, Multi-center, Randomized Controlled	Number:
Study to Evaluate the Safety and Efficacy of ARCR	REGENETEN.2020.01
augmented with REGENETEN™ Bioinductive Implant	Version: 2.0, 08 Dec
System in Full-thickness Tears (large or massive) Repair	2021
versus ARCR alone	Page: 87 of 134

the reason(s) for the termination or suspension. Circumstances that may warrant termination or suspension include, but are not limited to:

- Determination of unexpected, significant or unacceptable risk to participants
- Demonstration of efficacy that would warrant stopping
- Insufficient compliance with study protocol requirements
- Data that are not sufficiently complete and/or evaluable
- Determination of futility

Study may resume once concerns about safety, study protocol compliance, data quality are addressed and satisfy the Sponsor and IRB/IEC.

A specific study site in this multi-center study may also warrant termination under the following conditions:

- Non-compliance to GCP or protocol
- Failure to enroll subjects
- Major protocol deviations
- Inaccurate or incomplete data
- Unsafe or unethical practices
- Safety or performance considerations
- Investigator involuntarily discontinues participation in study

